## 6 Milestones

Milestone	Planned date
Start of data collection (FPFV)	Q1/Q2 2026
End of data collection (LPLV)	Q3/Q4 2029 The scheduled study duration per country includes a patient recruitment phase of up to 18 months and an individual prospective observational period for as long as feasible within the scheduled study timeframe. In case the observational period per country is prolonged, data collection will be prolonged as well.
Progress reports 	Progress reports related to the state of PASS recruitment will be part of every PSUR. The PSUR will be submitted as per the EURD list requirements.
Interim report	First interim report is expected in Q3/Q4 2028. Further interim analyses will be provided every two years unless the final report is delivered until Q4 2029.
Registration in the EU PAS register	Before start of data collection.
Final report of study results	December 2030 One year after end of data collection.

 Only if agreed with authorities.

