## **9 Research Methods**

### **9.1 Study Design**

This is a non-interventional, prospective, multicentre, multinational, cohort study based on primary data collection. Approximately 1,000 patients with documented uterine fibroids and symptoms such as HMB and with long-term Yselty® treatment in accordance with the SmPC will be included.

The study will be conducted in 5 European countries (Germany, Italy, Spain, Poland, and the UK), whereas the selection and sequence of countries may vary depending on the launch dates of Yselty®. For each country included in the study, the study start will be defined as after Yselty® has been authorised and made commercially available in that country. It is planned that Germany will be the first country to launch. The scheduled total study duration per country includes a recruitment phase of up to 18 months and an individual prospective observational period per patient for as long as feasible within the scheduled study timeframe. In case the observational period per country is prolonged, the data collection will be prolonged as well. The number of follow-up visits as per routine clinical practice for an individual patient will be dependent on the individual prospective observational period and are expected to be approximately every 12 months for this patient population. Visits to assess response to treatment will be more frequent at the beginning, and further visits may be required (depending on the country) to renew prescriptions approximately every 3 months.

Treatment with Yselty® will follow the physician's prescription according to the recommendations given in the SmPC. All decisions on therapeutic or diagnostic procedures, treatments, management of the indication, or resource utilisation will be at the full discretion of the treating physician without interference by the sponsor/MAH (referred to as MAH in the rest of this document) or study protocol. All treatment decisions will follow the real life treatment behaviour.

The assessment of BMD by DXA scans will be done as per routine clinical practice. For patients who received ABT from the initiation of Yselty®, the study results regarding BMD assessment will be contextualised with the real-world data available from literature for Ryeqo® at the time of the reports.

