  - Incidence rate of adverse events regarding electrocardiogram (ECG) findings indicative of QT interval prolongation, according to the physician's information
- For objective **II.h**:
  - Frequency of use of DXA scans in defined time periods:
    - Among patients with >1-year treatment, the number and proportion of Yselyt® users who received at least 1 DXA scan between 10 months until 14 months
    - Among patients with >2-year treatment, the number and proportion of Yselyt® users who received at least 2 DXA scans between 10 months until 26 months
    - Among patients with >3-year treatment, the number and proportion of Yselyt® users who received at least 3 DXA scans between 10 months until 38 months
    - Among patients with ≥4-year treatment, the number and proportion of Yselyt® users who received at least 4 DXA scans between 10 months until end of study
  - Frequency of DXA scans prior to treatment initiation in patients at high risk for osteoporosis or bone loss

---

 Additional analyses on ADRs will be performed.

 The RMP (see 15.1) contains targeted follow-up questionnaires for these events. Physicians who report these events will be asked to fill the corresponding targeted follow-up questionnaire.

 The RMP (see 15.1) contains targeted follow-up questionnaires for these events. Physicians who report these events will be asked to fill the corresponding targeted follow-up questionnaire.

 High risk patients will be identified by their treating physician as described in section 9.2.1.

- Number and proportion of patients who received Yselty® at a dose of 200 mg for more than 6 months without concomitant prescriptions for ABT at suitable time periods (e.g., 3-month intervals)
- For objective **II.i**:
  - Incidence rate of ADRs
  - Incidence rate of SADR
- For objective **II.j**:
  - Mean absolute and relative change in density (g/cm^2) and absolute value and relative change of BMD z-score and t-score from baseline (for patients with baseline DXA scan as per routine clinical practice – per SmPC only recommended for patients at high risk for osteoporosis or bone loss)

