### **9.5 Study Size**

Approximately 1,000 women of reproductive age with documented uterine fibroids and symptoms such as HMB being treated with Yselyt® long-term, according to the SmPC. This is a multinational study in 5 European countries (Germany, Italy, Spain, Poland and UK), whereas the selection and sequence of countries may change depending on the launch dates of Yselyt®. The number of study sites will vary per country, dependent on use of Yselyt®.

This is a descriptive study and is not intended to test a formal hypothesis. The sample size is based on feasibility and practical considerations rather than statistical. Sample size considerations are based on the primary endpoint, BMD z-score, which compares bone mineral density with a reference population of the same age and sex. The BMD z-score will

---

 Special situations include drug interactions, medication abuse, medication misuse, medication overdose, medication errors, unexpected therapeutic or clinical benefit from product use, pregnancy or lactation exposure with the product, lack of efficacy, off-label use, and occupational exposure (see section 11.4).

be measured at 3 sites for each patient, i.e., lumbar spine, total hip, and femoral neck and the lowest individual value is used to estimate the population proportion.

A single-group design was used to obtain a 2-sided 95% confidence interval (CI) for a single proportion. Given the standard normal distribution of BMD z-scores (z-distribution), the expected sample proportion of values < -2 (cutoff for low bone density) is assumed to be 2.5%, which corresponds to the lower 2.5% quantile of the z-distribution. With an effective sample size of 800 (assuming 20% dropout), the CI width at 12 months of follow-up is 2.2% and the expected precision of the proportion is 2.5%±1.1% (see Table 2). Assuming a further 20% yearly dropout rate, at 24 months of follow-up, the effective sample size is estimated to be 640 patients with a CI width of 2.4% and an expected precision of the proportion of 2.5%±1.2%. At 36 months of follow-up, the effective sample size is estimated to be 512 patients with a CI width of 2.8% and an expected precision of the proportion of 2.5%±1.4%. At 48 months of follow-up, the effective sample size is estimated to be 409 patients with a CI width of 3.0% and an expected precision of the proportion of 2.5%±1.5%.

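### Table 2's patient numbers at 36 and 48 months allow for dropout but not for the study's own calendar: 409 at month 48 is out of reach on the scheduled dates, and 512 at month 36 needs favourable assumptions

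*Protocol*

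**What the plan says.** Protocol Section 9.5 starts from 1,000 women ("Approximately 1,000 women of reproductive age with documented uterine fibroids") and describes its precision method thus: "A single-group design was used to obtain a 2-sided 95% confidence interval (CI) for a single proportion". The expected proportion with a z-score below -2 "is assumed to be 2.5%, which corresponds to the lower 2.5% quantile of the z-distribution". Losses enter only as annual dropout: "Assuming a further 20% yearly dropout rate, at 24 months of follow-up, the effective sample size is estimated to be 640 patients". The series ends with "At 48 months of follow-up, the effective sample size is estimated to be 409 patients with a CI width of 3.0" per cent. Table 2 lists 800, 640, 512 and 409 patients with half-widths of 1.10%, 1.20%, 1.35% and 1.50%, and its sample-size column names 20% annual dropout as the only assumption.

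The calendar is in Section 6. First visits begin in Q1/Q2 2026, last visits fall in Q3/Q4 2029, and "The scheduled study duration per country includes a patient recruitment phase of up to 18 months and an individual prospective observational period" limited by the study timeframe. Section 9.1 agrees: "The scheduled total study duration per country includes a recruitment phase of up to 18 months". The final report is dated December 2030, one year after data collection ends, and Section 12 repeats the 12-month interval. Data collection may be prolonged, but no date or trigger is given.

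Section 9.1.2 (objective II.h) has an endpoint for patients treated for four years or more: "users who received at least 4 DXA scans between 10 months until end of study". Table 1 has a month-48 column.

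**The concern.** Table 2 treats every enrolled woman as if she could be observed for 48 months unless she drops out. A woman enrolled near the end of an 18-month recruitment phase cannot be: observation stops at the last-visit date whether or not she is still in the study. This administrative censoring is missing from Section 9.5.

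The study exists to describe bone mineral density during long-term use. With no hypothesis test, expected precision is the only quantitative support for the study size. A regulator reading Table 2 would expect about 400 women with four-year data and half-widths near 1.5%. If the calendar yields far fewer, the stated long-term precision is wrong and the four-year DXA endpoint has few or no eligible patients.

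**Working it through.** **Step 1: reproduce Table 2.** Inputs from Section 9.5: N = 1,000, p = 0.025, 20% dropout a year, two-sided 95% interval.

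- n(m) = 1,000 × 0.8^(m/12) gives 800, 640, 512 and 409.6 at months 12, 24, 36 and 48.
- Half-width = 1.96 × √(0.025 × 0.975 / n) gives 1.08%, 1.21%, 1.35% and 1.51%.

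These match Table 2 after rounding. Its arithmetic is sound, and it contains dropout only.

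**Step 2: the span T from first to last visit.** The stated quarters run from 1 January to 30 June 2026 and from 1 July to 31 December 2029, so T lies between 36 and 48 months. A report in December 2030, one year after data collection ends, puts the end near December 2029 and narrows T to about 42 to 48 months.

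**Step 3: the share who can reach month m.** With enrolment spread uniformly over R months (an assumption) and first dose L months before enrolment (Table 1 counts from treatment start and allows L up to 3):

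share = (T − m + L) / R, held between 0 and 1; expected n = share × 1,000 × 0.8^(m/12).

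**Month 36 (Table 2: 512, ±1.35%)**

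| R | T | L | Share | n | Half-width |
|---|---|---|---|---|---|
| 18 | 42 | 0 | 6/18 | 171 | 2.34% |
| 18 | 48 | 0 | 12/18 | 341 | 1.66% |
| 18 | 42 | 3 | 9/18 | 256 | 1.91% |
| 18 | 48 | 3 | 15/18 | 427 | 1.48% |
| 12 | 42 | 0 | 6/12 | 256 | 1.91% |
| 12 | 48 | 0 | 12/12 | 512 | 1.35% |

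**Month 48 (Table 2: 409, ±1.50%)**

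| R | T | L | Share | n | Half-width |
|---|---|---|---|---|---|
| 18 | 42 to 48 | 0 | 0 | 0 | – |
| 18 | 48 | 3 | 3/18 | 68 | 3.70% |
| 12 | 48 | 3 | 3/12 | 102 | 3.02% |

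With the full three-month lead, any month-48 data require T above 45 months. Without a lead, even T = 48 admits only a woman enrolled on the first day. Bringing every enrolled woman to month 48 under 18-month recruitment needs 18 + 48 = 66 months, and to month 36 it needs 18 + 36 = 54.

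**Step 4: earlier rows.** At T = 42, the share at month 24 is (42 − 24)/18 = 1, so 640 stands. At month 12 the share is 1 throughout.

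**Step 5: earliest stated last-visit date.** If T were 36, month 36 would have about 0 patients (85 with the full lead, 3/18 × 512) and month 24 about 427 (12/18 × 640). This case fits poorly with the December 2030 report date.

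**The case against.** The best defence has four parts.

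**Prolongation.** Sections 6 and 9.1 and footnote 2 to Table 1 allow data collection to be extended. That matters for Table 1, which is titled an estimated schedule and already carries the clause. Table 2 does not carry it, and an extension with no date or trigger cannot support a specific count.

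**Recruitment may be quicker.** The text says up to 18 months. This stands for month 36: with 12-month recruitment and the longest span, 512 is reached exactly. It does not help month 48, which remains at 0 without a lead. Country starts that depend on launch dates work in the opposite direction.

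**Scan windows.** Section 9.7.3.4 uses ±6 months for the exploratory BMD-change analysis. Borrowing it adds 6 months to the numerator of the share. Month 36 then reaches 512 with R = 18 and T = 48. Month 48 reaches at most 9/12 × 409.6 = 307 even with the full lead, 12-month recruitment and the longest span, still below 409. Table 2 does not invoke this window.

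**The study is descriptive.** Its size rests on feasibility, and Section 9.9 warns of few observations in long-term users. Both are true and limit the seriousness. Section 9.9 attributes the shortage to uptake, DXA practice and missing measurements, however, and does not mention the calendar.

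A reader might infer more: that 512 at month 36 is impossible, that the 24-month row is also wrong, or that the primary analysis is undermined. The documents support none of these. The first fails under 12-month recruitment with the longest span. The second requires a 36-month span that sits badly with the report date, or staggered country starts whose size the protocol does not give. As to the third, the primary endpoint concerns treatment beyond 12 months, and even the 36-month span leaves 36 − 18 = 18 months for the last woman enrolled.

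**Conclusion.** The point holds for the two latest rows. On the scheduled dates, 409 patients at month 48 cannot occur: the expected number is 0, or at most about 68 with the full treatment lead and 102 with 12-month recruitment as well. At month 36, uniform 18-month recruitment gives about 171 to 341, or up to about 427 with the full lead. The stated 512 is a favourable case rather than an expectation.

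These figures rest on the protocol's 20% annual dropout, uniform accrual, an end of data collection near December 2029 and no prolongation. The 12-month row stands, and the 24-month row stands unless the last visit falls early or country starts are staggered. This is an inconsistency between schedule and sample size in a descriptive study. It should be fixed, but it does not threaten the primary analysis.

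**What to change.** Recompute the 36- and 48-month rows of Section 9.5 and Table 2 with staggered entry and the planned last-visit date as well as dropout, and state the accrual assumption. Delete the 48-month row, or label it as attainable only if data collection is prolonged. Label the four-year DXA endpoint under objective II.h in Section 9.1.2 in the same way. Table 1 needs no change, because its footnote already carries the condition.

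The cost is a text edit and one revised table. The stated long-term precision becomes less favourable, and no extra patients are needed.

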#### **9.7.3.3 Analysis of Primary Endpoint**

The primary objective will only be assessed in users with the long-term treatment (>12 months) and where z-scores of lumbar spine, total hip, or femoral neck are available. For rates of events of BMD z-scores below the age-related threshold of -2 standard deviations, the number and percentage of patients with these events will be provided including 95% CIs.

The aggregated number, frequency of DXA scans, anatomic site of DXA scan, machine type, and imaging parameters of DXA scans during the observational period will be analysed by descriptive statistics. If results of DXA scans can be interpreted in a categorised way, shift tables for the change from baseline, will be provided, where available. If images of the DXA scans can be provided by the doctors, they will be reviewed by 1 independent expert for their suitability and included in an additional sensitivity analysis.

Sensitivity analyses using different criteria (e.g., machine type) to select DXA scans that ensure their comparability will be performed to evaluate the primary endpoint if the sample size allows (e.g., if more than 30 patients remain after selection of suitable cases) and will be further detailed in the SAP.

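### The planning confidence intervals in Protocol section 9.5 and Table 2 are symmetric Wald intervals for a rare proportion, so both limits sit too low and the upper limit is understated by about 0.2 to 0.5 percentage points

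*Protocol*

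**What the plan says.** Protocol section 9.5 describes the calculation this way: "A single-group design was used to obtain a 2-sided 95% confidence interval (CI) for a single proportion". The input is that "the expected sample proportion of values < -2 (cutoff for low bone density) is assumed to be 2.5" per cent. With 20% yearly dropout from 1,000 women, the section goes through four time points:

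- 12 months: "With an effective sample size of 800 (assuming 20% dropout), the CI width at 12 months of follow-up is 2.2" per cent
- 24 months: "the effective sample size is estimated to be 640 patients with a CI width of 2.4" per cent
- 36 months: "the effective sample size is estimated to be 512 patients with a CI width of 2.8" per cent
- 48 months, with 409 women: "a CI width of 3.0% and an expected precision of the proportion of 2.5%±1.5" per cent

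Table 2 repeats these as half-widths of 1.10, 1.20, 1.35 and 1.50 points, with 95% limits of 1.4-3.6%, 1.3-3.7%, 1.1-3.9% and 1.0-4.0%. The interval method is not named. Section 9.5 also states that the study is descriptive, tests no hypothesis and is sized on feasibility. For the analysis, section 9.7.3.3 promises a number and percentage with 95% CIs and again names no method.

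**The concern.** A plus-or-minus interval for a proportion near zero treats the sampling distribution as symmetric. With an expected count of 10 to 20 it is not. Given the same observed percentage, the data are compatible with values further above it than below it, so a symmetric interval is shifted down as a whole.

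In a safety study the upper limit gets the attention, since it shows how large a frequency of low bone density remains compatible with the data. Table 2 is the protocol's only numerical statement of precision for the primary endpoint. If its upper limits are too low, the precision looks slightly more reassuring than the protocol's own n and p support. The gap is widest at the later time points, which matter most for long-term use.

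**Working it through.** **Inputs, all from section 9.5 and Table 2.** p = 0.025; two-sided 95%, so z = 1.96; n = 800, 640, 512, 409.

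**Step 1: reproduce the printed figures.** Wald half-width = z × √(p(1−p)/n), with p(1−p) = 0.025 × 0.975 = 0.024375.

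- n = 800: 1.96 × √(0.024375/800) = 1.08 points, limits 1.42-3.58%
- n = 640: 1.21 points, limits 1.29-3.71%
- n = 512: 1.35 points, limits 1.15-3.85%
- n = 409: 1.96 × √(0.024375/409) = 1.51 points, limits 0.99-4.01%

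These match Table 2 to rounding. A continuity-corrected Wald interval (half-widths 1.14, 1.29, 1.45, 1.64) does not match. Wilson and Clopper-Pearson limits are asymmetric and do not match either. Table 2 is therefore plain Wald. The 36-month text (±1.4, width 2.8) differs from the table (±1.35) only by rounding; the unrounded width is 2.70.

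**Step 2: expected cases.** n × p = 20, 16, 12.8 and 10.2.

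**Step 3: recompute without the symmetry assumption.** With x cases in n:

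- Clopper-Pearson: lower = Beta quantile(0.025; x, n−x+1), upper = Beta quantile(0.975; x+1, n−x), using the whole counts 20, 16, 13 and 10.
- Wilson: centre (p + z²/2n)/(1 + z²/n), half-width z√(p(1−p)/n + z²/4n²)/(1 + z²/n), at p = 0.025.

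| n | Table 2 | Clopper-Pearson | Wilson | Exact minus printed, upper | Exact minus printed, lower |
|---|---|---|---|---|---|
| 800 | 1.4-3.6% | 1.53-3.83% | 1.62-3.83% | 0.23 | 0.13 |
| 640 | 1.3-3.7% | 1.44-4.03% | 1.54-4.02% | 0.33 | 0.14 |
| 512 | 1.1-3.9% | 1.36-4.30% | 1.46-4.25% | 0.40 | 0.26 |
| 409 | 1.0-4.0% | 1.18-4.45% | 1.37-4.51% | 0.45 | 0.18 |

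Ten of 409 is 2.44%, slightly under the assumed value. At the non-integer count 10.2 the exact upper limit is 4.52%, about 0.5 above the printed figure.

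**Step 4: how often each Wald limit misses.** Summing binomial probabilities over all x at a true p of 2.5%:

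| n | Upper limit below truth | Lower limit above truth | Total coverage |
|---|---|---|---|
| 800 | 3.73% | 1.24% | 95.03% |
| 640 | 4.14% | 1.21% | 94.65% |
| 512 | 5.77% | 1.11% | 93.13% |
| 409 | 5.68% | 0.81% | 93.50% |

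Nominal is 2.5% on each side. The Clopper-Pearson upper limit misses in 2.02%, 2.08%, 1.15% and 2.40% of samples. Total coverage looks acceptable because too many misses at the top are partly offset by too few at the bottom.

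**The case against.** The strongest reply is that these are planning figures in a descriptive study sized on feasibility. Table 2 reports expected precision around an assumed value, and no margin or threshold depends on it. Its half-widths (1.10, 1.20, 1.35, 1.50) are not far from half the exact widths (1.15, 1.30, 1.47, 1.64), and total coverage is close to nominal. All of this stands and limits the weight of the point. It does not make the printed limits right.

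A reader might go further in four ways that the protocol does not support.

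- **That the analysis itself will use Wald intervals.** Section 9.7.3.3 names no method, and section 9.7.1 leaves statistical detail to the SAP. Leaving the choice there is legitimate.
- **That intervals will collapse in small subsets.** Section 9.7.3.3 allows sensitivity analyses "if the sample size allows (e.g., if more than 30 patients remain after selection of suitable cases"). At n = 31 and p = 2.5%, no cases occur in 0.975^31 = 46% of samples; a Wald interval then has zero width and its coverage is 54%. That holds only if Wald were reused and p were 2.5%. Section 9.5 takes the lowest of three sites, which implies a higher p; with independent sites, an upper bound, p would be 6.7-7.3% and the chance of no cases 9-12%. A coverage of 85% at n = 136 likewise assumes Wald, and also an equal three-way split of 409 women that the protocol nowhere states.
- **That the figure of 30 should give way to a floor of about 200 women.** The 30 is an example for optional DXA-comparability analyses. A much higher floor is a preference, and given the few BMD observations that section 9.9 warns of, it could remove those analyses altogether.
- **That the protocol claims to rule out 3.6% or 4.0%.** It makes no such claim.

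**Conclusion.** The point holds for the planning intervals in section 9.5 and Table 2 only. They are Wald intervals for a proportion with 10 to 20 expected cases. Both limits are too low: the upper by about 0.2 points at n = 800, rising to about 0.5 at n = 409, and the lower by 0.1 to 0.3 points against exact limits. The upper limit misses a true 2.5% in 3.7% to 5.8% of samples, against a nominal 2.5%.

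This takes the protocol's own assumptions as given: p = 2.5%, the stated effective sample sizes, and a usable z-score for every woman counted. It is a modest correction to printed error bars. It changes neither the sample size nor any decision, and it says nothing about the method the analysis will use.

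**What to change.** Recompute Table 2 and the matching sentences of section 9.5 with Wilson or Clopper-Pearson limits, and name the method there. Print the lower and upper limits, and drop the symmetric half-width, which cannot describe a skewed interval. With Clopper-Pearson the four rows become 1.5-3.8%, 1.4-4.0%, 1.4-4.3% and 1.2-4.5%. Restating the text also removes the rounding difference at 36 months.

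The cost is one table and a few figures in one paragraph. The stated upper limits become slightly less favourable, and nothing else in the design changes.
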